7.5.1 Retained Samples for Bioavailability/Bioequivalence

Not applicable.

7.6 Treatment Compliance

Treatment compliance for all study treatments will be monitored by drug accountability, medical record, and electronic Case Report Form (eCRF). Drug accountability should be reviewed by the study-site staff at each visit to confirm treatment compliance.

7.7 Concomitant Therapy

Concomitant medications are recorded at baseline and throughout the treatment phase of the study in the appropriate section of the eCRF. All medications (prescriptions or over-the-counter medications) continued at the start of the study or started during the study and different from the study treatment must be documented in the concomitant therapy section of the eCRF.

7.7.1 Prohibited and/or Restricted Treatments

Prohibited and/or restricted medications taken prior to and during study treatment administration in the study are described below. Medications taken within 2 weeks prior to study treatment administration must be recorded on the CRF.

7.7.1.1 Prohibited Treatments

The following medications are prohibited during the study:

- LAG-3 targeting agents.

- Any botanical preparation (eg, herbal supplements or traditional Chinese medicines) intended to treat the disease under study or provide supportive care. Use of marijuana and its derivatives for treatment of symptoms related to cancer or cancer treatment are permitted if obtained by medical prescription or if its use (even without a medical prescription) has been legalized locally.
- Immunosuppressive agents (except used to treat a drug-related AE).
- Immunosuppressive doses of systemic corticosteroids (except as stated in Section 7.7.2).
- Any concurrent anti-neoplastic therapy (ie, chemotherapy, hormonal therapy, immunotherapy, extensive, non-palliative radiation therapy, or standard or investigational agents for treatment of malignancy)
- Any live / attenuated vaccine (eg, varicella, zoster, yellow fever, rotavirus, oral polio and measles, mumps, rubella [MMR]) during treatment and until 100 days after last dose. Inactivated vaccines are permitted.

7.7.1.2 Imaging Restriction and Precautions

It is the local imaging facility's responsibility to determine, based on participant attributes (eg, allergy history, diabetic history, and renal status), the appropriate imaging modality and contrast regimen for each participant. Imaging contraindications and contrast risks should be considered in this assessment. Participants with renal insufficiency should be assessed as to whether or not they should receive contrast and if so, what type and dose of contrast is appropriate. Specific to MRI, participants with severe renal insufficiency (ie, estimated glomerular filtration rate [eGFR] < 30 mL/min/1.73 m²) are at increased risk of nephrogenic systemic fibrosis. MRI contrast should not be given to this participant population. In addition, participants are excluded from MRI if they have tattoos, metallic implants, pacemakers, etc.

The ultimate decision to perform MRI in an individual participant in this study rests with the site radiologist, the investigator, and the standard set by the local Ethics Committee.

7.7.2 Permitted Therapy

Participants are permitted the use of topical, ocular, intra-articular, intranasal, and inhalational corticosteroids (with minimal systemic absorption). Adrenal replacement steroid doses > 10 mg daily prednisone equivalent are permitted. A brief (less than 3 weeks) course of corticosteroids for prophylaxis (eg, contrast dye allergy) or for treatment of non-autoimmune conditions (eg, delayed-type hypersensitivity reaction caused by a contact allergen) is permitted.

7.7.2.1 Palliative Therapy

Palliative (limited-field) radiation therapy and palliative surgical resection are permitted if the following criteria are met:

- The participant is considered to have progressed at the time of palliative therapy and meets criteria to continue with treatment beyond progression (Section 8.1.2.2).
- The case is discussed with the BMS Medical Monitor/designee. Palliative therapy must be clearly documented as such in the study record.

Participants should not receive study treatment during radiation as the potential for overlapping toxicities with radiotherapy and BMS-986213 or with radiotherapy and nivolumab is currently not known. Anecdotal data suggest that radiotherapy administered to participants while receiving nivolumab therapy is tolerable. However, because concurrent radiotherapy and immunotherapies in cancer have not been formally evaluated, in cases where palliative radiotherapy is required for a tumor lesion, then all study treatments should be withheld for at least 1 week before, during, and 1 week after radiation. Participants should be closely monitored for any potential toxicity during and after receiving radiotherapy, and AEs related to radiotherapy should resolve to Grade 1 prior to resuming study treatment.

7.7.2.2 Surgical Resection Following Initial Response

Investigators may choose to resect solitary lesions in participants with unresectable or metastatic melanoma and render the participant free of macroscopic disease. Participants enrolled in this study may have lesions surgically resected only following consultation with the BMS Medical Monitor/designee and following the Week 20 efficacy assessments. If tumor shrinkage of the solitary lesion is noted on the re-staging assessment (eg, Week 20), it is highly encouraged that surgical resection be delayed until subsequent scans fail to demonstrate further shrinkage. Participants with a PR who go on to have surgical resection of remaining disease will be considered a PR. Tumor tissue of any resected solitary lesion should be submitted to BMS (see [Section 9.8.2](#)). Detailed instructions on the obtaining, processing, labeling, handling, storage, and shipment of these specimens will be provided in a separate procedure manual at the time of study initiation.

7.7.3 Treatment of Infusion-Related Reactions

Because both relatlimab and nivolumab contain only human immunoglobulin protein sequences, they are unlikely to be immunogenic and induce infusion or hypersensitivity reactions. However, if such a reaction were to occur, it might manifest with fever, chills, rigors, headache, rash, pruritus, arthralgias, hypotension, hypertension, bronchospasm, or other allergic-like reactions. All Grade 3 or 4 infusion reactions should be reported within 24 hours to the BMS Medical Monitor/designee and reported as an SAE if it meets the criteria. Infusion reactions should be graded according to NCI CTCAE (Version 5.0) guidelines.

Treatment recommendations are provided below and may be modified based on local treatment standards and guidelines, as appropriate:

For Grade 1 symptoms: (mild reaction; infusion interruption not indicated; intervention not indicated):

- Remain at bedside and monitor participant until recovery from symptoms. The following prophylactic premedications are recommended for future infusions: diphenhydramine 50 mg (or equivalent) and/or acetaminophen/paracetamol 325 to 1000 mg at least 30 minutes before additional nivolumab administrations

For Grade 2 symptoms: (moderate reaction required therapy or infusion interruption but responds promptly to symptomatic treatment (eg, antihistamines, non-steroidal anti-inflammatory drugs, narcotics, corticosteroids, bronchodilators, IV fluids); prophylactic medications indicated for ≤ 24 hours):

- Stop the study treatment infusion, begin an IV infusion of normal saline, and treat the participant with diphenhydramine 50 mg IV (or equivalent) and/or acetaminophen/paracetamol 325 to 1000 mg; remain at bedside and monitor participant until resolution of symptoms. Corticosteroid and/or bronchodilator therapy may also be administered as appropriate. If the infusion is interrupted, then restart the infusion at 50% of the original infusion rate when symptoms resolve; if no further complications ensue after 30 minutes, the rate may be increased to 100% of the original infusion rate. Monitor participant closely. If symptoms recur, then no further study treatment will be administered at that visit.
- For future infusions, the following prophylactic premedications are recommended: diphenhydramine 50 mg (or equivalent) and/or acetaminophen/paracetamol 325 to 1000 mg should be administered at least 30 minutes before infusion. If necessary, corticosteroids (up to 25 mg of hydrocortisone or equivalent) may be used.

For Grade 3 or 4 symptoms: (severe reaction, Grade 3: prolonged [ie, not rapidly responsive to symptomatic medication and/or brief interruption of infusion]; recurrence of symptoms following initial improvement; hospitalization indicated for other clinical sequelae [eg, renal impairment, pulmonary infiltrates]; Grade 4: Life-threatening; pressor or ventilatory support indicated):

- Immediately discontinue infusion of study treatment. Begin an IV infusion of normal saline and treat the participant as follows: Recommend bronchodilators, epinephrine 0.2 to 1 mg of a 1:1000 solution for subcutaneous administration or 0.1 to 0.25 mg of a 1:10,000 solution injected slowly for IV administration, and/or diphenhydramine 50 mg IV with methylprednisolone 100 mg IV (or equivalent), as needed. Participant should be monitored until the investigator is comfortable that the symptoms will not recur. Study treatment will be permanently discontinued. Investigators should follow their institutional guidelines for the treatment of anaphylaxis. Remain at bedside and monitor participant until recovery of the symptoms.

In case of late-occurring hypersensitivity symptoms (eg, appearance of a localized or generalized pruritus within 1 week after treatment), symptomatic treatment may be given (eg, oral antihistamine or corticosteroids).

7.8 Treatment After the End of the Study

At the conclusion of the study, participants who continue to demonstrate clinical benefit will be eligible to receive BMS-supplied study treatment for the maximum treatment duration specified in [Section 5.3](#). Study treatment will be provided via an extension of the study, a rollover study requiring approval by responsible health authority and ethics committee, or through another mechanism at the discretion of BMS. BMS reserves the right to terminate access to BMS supplied study treatment if any of the following occur: a) the study is terminated due to safety concerns; b)

the development of relatlimab is terminated for other reasons, including but not limited to lack of efficacy and/or not meeting the study objectives; c) the participant can obtain medication from a government-sponsored or private health program. In all cases BMS will follow local regulations.

8 DISCONTINUATION CRITERIA

8.1 Discontinuation from Study Treatment

Participants **MUST** discontinue investigational product (and non-investigational product at the discretion of the investigator) for any of the following reasons:

- Participant's request to stop study treatment. Participants who request to discontinue study treatment will remain in the study and must continue to be followed for protocol specified follow-up procedures. The only exception to this is when a participant specifically withdraws consent for any further contact with him/her or persons previously authorized by participant to provide this information.
- Any clinical AE, laboratory abnormality or intercurrent illness which, in the opinion of the investigator, indicates that continued participation in the study is not in the best interest of the participant
- Termination of the study by BMS
- Loss of ability to freely provide consent through imprisonment or involuntarily incarceration for treatment of either a psychiatric or physical (eg, infectious disease) illness. (Note: Under specific circumstances, a participant who has been imprisoned may be permitted to continue as a participant. Strict conditions apply and BMS approval is required.)
- Additional protocol-specified reasons for discontinuation ([Section 8.1.1](#))

In the case of pregnancy, the investigator must immediately, within 24 hours of awareness of the pregnancy, notify the BMS medical monitor or designee of this event. In most cases, the study treatment will be permanently discontinued in an appropriate manner (eg, dose tapering if necessary for participant safety). Refer to [Section 9.2.5](#), Pregnancy.

Refer to the Schedule of Activities for data to be collected at the time of treatment discontinuation and follow-up and for any further evaluations that can be completed.

All participants who discontinue study treatment should comply with protocol specified follow-up procedures as outlined in [Section 2](#). The only exception to this requirement is when a participant withdraws consent for all study procedures including post-treatment study follow-up or loses the ability to consent freely (ie, is imprisoned or involuntarily incarcerated for the treatment of either a psychiatric or physical illness).

If study treatment is discontinued prior to the participant's completion of the study, the reason for the discontinuation must be documented in the participant's medical records and entered on the appropriate eCRF page.

8.1.1 Dose Discontinuation

If a participant in any of the nivolumab/relatlimab combination arms meets criteria for discontinuation in [Table 7.4-1](#), the participant must discontinue both nivolumab and relatlimab and be taken off the treatment phase of the study.

Nivolumab and relatlimab treatment must be permanently discontinued per criteria in [Table 7.4-1](#) in [Section 7.4](#) (Dosage Modification). Discontinue from study treatment for any AE, laboratory abnormality, or intercurrent illness that, in the judgment of the investigator, presents a substantial clinical risk to the participant with continued nivolumab or relatlimab dosing.

Study treatment must also be permanently discontinued for the following:

- Any event that leads to delay in dosing lasting > 8 weeks from the previous dose requires discontinuation, with the following exceptions:
- Dosing delays to allow for prolonged steroid tapers to manage drug-related AEs are allowed.
- Dosing delays lasting > 8 weeks from the previous dose that occur for non-drug-related reasons may be allowed if approved by the BMS Medical Monitor (or Clinical Scientist).
- Tumor assessments should continue as per protocol even if dosing is delayed. Periodic study visits to assess safety and laboratory studies should also continue every 6 weeks or more frequently if clinically indicated during such dosing delays.

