Laboratory Tests	X	Hematology, Serum Chemistry, and Urinalysis as outlined in Table 9.4.4-1 within 14 days of randomization . Serology as outlined in Table 9.4.4-1 within 28 days of randomization . For HIV: testing at sites where locally mandated, see Appendix 8 .
Troponin	X	Within 14 days prior to randomization.
ECG	X	Within 14 days prior to randomization.
Pregnancy Test (WOCBP only)	X	Serum or urine (minimum sensitivity equivalent units 25 IU/L or equivalent units of HCG).
Follicle-stimulating hormone (FSH)	X	If needed to document post-menopausal status as defined in Table 9.4.4-1 .
Efficacy Assessments		
Body Imaging	X	Contrast-enhanced CT of the chest, abdomen, pelvis, and all known sites of disease within 28 days prior to randomization. See Table 9.1.2-1 for preferred and alternative imaging methods.
Brain Imaging	X	MRI of the brain without and with contrast is required for ALL participants during screening to rule out brain metastases within 28 days prior to randomization. CT of the brain (without and with contrast) can be performed if MRI is contraindicated. See Table 9.1.2-1 for preferred and alternative imaging methods.

Table 2-2: On-Study Assessments (CA224047)

Procedure ^a	Day 1 of each cycle (Cycle = 4 weeks)	Other Time Points Relative to Dosing Schedule	Notes
Safety Assessments			
Inclusion/Exclusion Criteria		X	All inclusion/exclusion criteria should be confirmed prior to randomization.
Targeted Physical Examination	X		To be performed only as clinically indicated within 3 calendar days prior to dosing.
Vital Signs	X		Including BP, heart rate, and temperature within 3 calendar days prior to dosing.
Physical Measurements (including performance status)	X		Weight and ECOG Performance Status/Lansky Performance Score for minors ONLY (see Appendix 6) within 3 calendar days prior to dosing.
Adverse Events Assessment	Continuously		All AEs (SAEs or non-serious AEs), including those associated with SARS-CoV-2 infection, must be collected continuously during the treatment period.
Concomitant Medication Assessment	Continuously		
Laboratory Tests	X		Within 3 calendar days prior to dosing including Hematology, Serum Chemistry, Urinalysis as outlined in Table 9.4.4-1 . All labs should be checked prior to dosing.

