7.1.1 BMS-986213 or Nivolumab Dosing

BMS-986213 (prepared in normal saline for relatlimab 160 mg/nivolumab 480 mg) or nivolumab 480 mg dosing is to be administered as an IV infusion through a 0.2-micron to 1.2-micron pore-size, low-protein binding in-line filter at the protocol-specified doses. It is not to be administered as an IV push or bolus injection. Instructions for dilution and infusion of relatlimab/nivolumab or nivolumab injection will be provided in the pharmacy binder. Care must be taken to assure sterility of the prepared solution as the product does not contain any antimicrobial preservative or bacteriostatic agent.

Participants should receive BMS-986213 or nivolumab as a 1-hour infusion on Day 1 of each treatment cycle until progression, unacceptable toxicity, withdrawal of consent, or the study ends,

whichever occurs first. Participants should begin study treatment within 3 calendar days of randomization.

The sponsor, participants, investigator, and site staff will be blinded to the study drug administered. Each investigative site must assign an unblinded pharmacist/designee.

There will be no dose escalations or reductions of any study treatment allowed. Participants may be dosed within a ± 3 day window (ie, participants may be dosed no less than 25 days and no more than 31 days between doses). Premedication is not recommended for the first dose of either treatment.

Participants should be carefully monitored for infusion reactions during administration. If an acute infusion reaction is noted, participants should be managed according to [Section 7.7.3](#).

Doses may be interrupted, delayed, or discontinued depending on how well the participant tolerates the treatment. Dosing visits must not be skipped, only delayed.

Infusions are compatible with polyvinyl chloride (PVC) or polyolefin containers and infusion sets, and glass bottles.

Care must be taken to assure sterility of the prepared solution as the product does not contain any antimicrobial preservative or bacteriostatic agent.

For details on prepared drug storage, preparation, and administration, please refer to the IBs and/or pharmacy binder.

The selection and timing of dose for each participant is provided in [Table 7.1-1](#).

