7.4.2 Dose Delay Criteria

Dose delay criteria apply for all drug-related AEs. Delay treatment administration if any of the delay criteria in [Table 7.4-1](#) are met. Delay dosing for any adverse event, laboratory abnormality, or intercurrent illness which, in the judgment of the investigator, warrants delaying the dose of study medication.

Study treatment must also be delayed for SARS-CoV-2 infection, either confirmed or suspected.

For participants who require delay of study drug, re-evaluate weekly, or more frequently, if clinically indicated and resume treatment when retreatment criteria are met (see [Section 7.4.3](#)). Continue tumor assessments per protocol even if dosing is delayed.

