7.4.3 Criteria to Resume Treatment

Participants may resume treatment with study drug if they have completed AE management (ie, corticosteroid taper) or are on ≤ 10 mg prednisone or equivalent, and meet the requirements per [Table 7.4-1](#).

Prior to re-initiating treatment in a participant with a dosing delay lasting > 8 weeks, the Medical Monitor (or Clinical Scientist) must be consulted. Continue tumor assessments per protocol even if dosing is delayed. Continue periodic study visits to assess safety and laboratory studies weekly or more frequently if clinically indicated during such dosing delays.

In the event of treatment delay due to SARS-CoV-2 infection (confirmed or suspected), participants with may resume treatment after all of the following: 1) at least 10 days (20 days for severe/critical illness) have passed since symptoms first appeared or positive test result (eg, RT-PCR or viral antigen); 2) resolution of acute symptoms (including at least 24 hours has passed since last fever without fever-reducing medications); 3) evaluation by the investigator with confirmation that there are no sequelae that would place the participant at a higher risk of receiving investigational treatment; and 4) consultation by the Medical Monitor. For suspected cases, treatment may also resume if SARS-CoV-2 infection is ruled out and other criteria to resume treatment are met.

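### Section 8.1.1 lets safety and laboratory visits fall to every 6 weeks during permitted dosing delays beyond 8 weeks, where Section 7.4.3 requires them weekly

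*Protocol*

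**What the plan says.** Section 8.1.1 gives the general rule: "Any event that leads to delay in dosing lasting > 8 weeks from the previous dose requires discontinuation". It then lists exceptions. One reads "Dosing delays to allow for prolonged steroid tapers to manage drug-related AEs are allowed"; another covers delays for reasons unrelated to drug, with approval from the Medical Monitor or Clinical Scientist. For delays permitted in this way, it says that safety visits and "laboratory studies should also continue every 6 weeks or more frequently if clinically indicated during such dosing delays".

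Section 7.4.3 requires Medical Monitor or Clinical Scientist consultation before re-dosing after a delay of more than 8 weeks, and then says: "Continue periodic study visits to assess safety and laboratory studies weekly or more frequently if clinically indicated during such dosing delays". The section also reaches steroid tapers: "Participants may resume treatment with study drug if they have completed AE management (ie, corticosteroid taper", or when the prednisone-equivalent dose is 10 mg or less.

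Section 7.4.2 applies to every delay: "For participants who require delay of study drug, re-evaluate weekly, or more frequently, if clinically indicated". It does not name laboratory studies.

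For participants dosed on schedule, Section 7.1.1 says "participants may be dosed no less than 25 days and no more than 31 days between doses", and Table 2-2 places the laboratory panel as follows: "Within 3 calendar days prior to dosing including Hematology, Serum Chemistry, Urinalysis as outlined in" Table 9.4.4-1. Footnote a of Table 2-2 moves a cycle's procedures along with a delayed dose, exempting only body imaging and pregnancy testing.

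**The concern.** Two operative sections give different minimum frequencies for the same visits in the same kind of delay. The sparser one sits in the section that authorises the long delay, which is where a site would naturally look. Many of the participants concerned will be held for drug-related toxicity and on a prolonged steroid taper, so they have a clear reason for close laboratory follow-up.

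On the visible text, a site following 8.1.1 could test such a participant less often than one who is well and receiving drug every 4 weeks. The clause allowing more visits when clinically indicated appears in both sentences. It permits extra visits but does not raise the 6-week minimum. The protocol gives no reason for choosing 6 weeks.

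What is at stake is safety monitoring in a small group. Efficacy inference is not involved.

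**Working it through.** The plan has no derived figure to reproduce here. The check compares stated intervals.

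**Inputs**

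| Quantity | Value | Source (Protocol) |
|---|---|---|
| Visit interval, excepted delays | 6 weeks | 8.1.1 |
| Visit interval, delays over 8 weeks | 1 week | 7.4.3 |
| Re-evaluation interval, any delay | 1 week, laboratory studies not named | 7.4.2 |
| Cycle length | 4 weeks | Table 2-2 |
| Gap between doses on schedule | 25 to 31 days | 7.1.1 |
| Laboratory tests before each dose | 0 to 3 days | Table 2-2 |

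**8.1.1 against 7.4.3**

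- Intervals: 6 × 7 = 42 days against 7 days; 42 / 7 = 6.
- Minimum visits per 6 weeks of delay: 6 / 6 = 1 under 8.1.1 and 6 / 1 = 6 under 7.4.3, a difference of 5.
- Illustration over 12 weeks at each interval: 12 / 6 = 2 visits against 12 / 1 = 12.

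**8.1.1 against on-schedule testing**

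- Nominal cycle of 28 days: 42 − 28 = 14 days longer.
- Dosing window: 42 − 31 = 11 and 42 − 25 = 17, so 11 to 17 days longer (ratios 42 / 31 = 1.35 and 42 / 25 = 1.68).
- Allowing for the 3-day laboratory window, consecutive on-schedule tests can be 25 − 3 = 22 to 31 + 3 = 34 days apart. Even against the longest of these, 42 − 34 = 8 days longer.

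**Does another provision restore a laboratory minimum?**

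- Table 2-2 does not, because footnote a carries the laboratory panel forward with the delayed dose. Pregnancy testing, by contrast, keeps its 4-week rhythm whatever the dosing schedule.
- Continuous adverse event assessment (Table 2-2) and proactive follow-up (Section 9.2.3) state no laboratory interval.
- The Appendix 9 algorithms are guidance and their figures are not shown, so nothing is assumed about intervals in them.

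**Do the two sections cover the same delays?** Section 8.1.1 counts from the previous dose. Section 7.4.3 does not say where its count starts.

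- If 7.4.3 also counts from the previous dose, the sections overlap for every excepted delay.
- If it counts from the missed scheduled dose, as SAP Section 7.4.2.1 does when defining a delay, its threshold is about 4 + 8 = 12 weeks from the previous dose. The conflict is then certain beyond about 12 weeks. Between 8 and 12 weeks, 7.4.2 still requires weekly re-evaluation, without naming laboratory studies.

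**The case against.** The strongest reply is that the protocol, read as a whole, already requires weekly contact. Section 7.4.2 covers every delay, 7.4.3 names laboratory studies, and weekly visits breach nothing in 8.1.1. Harm needs a site to read 8.1.1 alone, and nothing in the documents shows that any site has. This stands, and it limits the point to an inconsistency. It does not justify an operative minimum that falls short of two other sections.

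The two thresholds are also worded differently, so the 42-against-7 contrast may not apply to every excepted delay. That is fair, and the 8-to-12-week band is ambiguous for laboratory tests. The clash beyond about 12 weeks remains on either reading.

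The on-schedule comparison can be called selective, because Table 2-2 tests are pre-dose checks. After treatment ends, Table 2-3 tests at 30 days and again at 100 days only if treatment-related toxicity persists, and that 70-day gap is longer than 42 days. This is correct, but those participants have stopped drug for good, while participants in an excepted delay are being considered for re-dosing. The conflict with 7.4.3 does not depend on this comparison.

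Table 7.4-1 makes resumption after several toxicities depend on laboratory values, for example liver tests at baseline or creatinine at Grade 1 or below or baseline. Repeat testing is therefore needed before restart. That governs the decision to re-dose but sets no frequency during the hold.

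Finally, weekly visits may be more than an approved delay unrelated to drug needs. A tiered rule is possible, but 7.4.3 draws no such distinction now and would have to change as well.

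**Conclusion.** The concern holds. Section 8.1.1 states a 42-day minimum for safety and laboratory visits where 7.4.3 states 7 days, and 42 days is at least 8 days longer than any laboratory gap allowed on schedule. The protocol does contain the stricter rule, so the fault is one wrong number among otherwise consistent provisions. It should be corrected, although nothing in the primary or secondary analyses turns on it.

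The size of the conflict rests on reading each interval as a minimum. Its full extent, from 8 weeks onward, also rests on 7.4.3 counting delay from the previous dose; otherwise it is certain only from about 12 weeks. The documents do not give the number of participants with such delays. The SAP records that the primary analysis took place in March 2021, so the practical benefit is for participants still on treatment or in any extension under Protocol Section 7.8.

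**What to change.** In Protocol Section 8.1.1, replace the 6-week interval for safety and laboratory visits with a weekly one, keeping the allowance for more frequent visits when clinically indicated, so that it matches 7.4.3. Send sites a short memo stating that weekly applies to all delays permitted under 8.1.1.

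The cost is one phrase of protocol text and the memo. A site already following 7.4.3 sees no change. A site that has used 6 weeks would add up to 6 − 1 = 5 visits per participant for each 6 weeks of excepted delay. No statistical section of the protocol or SAP needs to change.
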